15.1 General Statistical Considerations

- Type I error for hypothesis testing will be $\alpha = 0.05$, and 95% confidence intervals will be used for parameter estimation, unless otherwise specified. Type II error will be based on $\beta = 0.10$, unless otherwise specified. Only the primary analysis will use an adjustment for multiple comparisons.
- Summary statistics for continuous variables will include (but may not be limited to) the number of observations, mean, standard deviation, minimum, median and maximum. For categorical variables, summary statistics will include (but may not be limited to) counts, percentages, and cross-tabulation tables.
- Standard diagnostics will be performed to assess whether the assumptions for specific parametric statistical methods are adequately supported by the data. Should parametric methods be inappropriate, the analogous non-parametric methods will be used and only these results will be reported.
- Imputation of missing values will not be applied.
- No interim analyses for efficacy or futility are planned, although the trial may be stopped early based on observations from continual safety monitoring.
- Data analysis will be conducted using SAS® v9.4 (or later).

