15.5 Analysis for the Primary Objective

The co-primary objectives of this study are to test superior treatment efficacy of Imiquimod + HPV vaccine (Trt1) compared to control (Trt0), and likewise Imiquimod only (Trt2) compared to control (Trt0). The primary outcome is *histologic regression* (yes/no) after completion of the 12 to 16 weeks imiquimod course. The full definition of *histologic regression* and how it is determined is described in Section 5.1.

The co-primary hypothesis tests are:

 $\{H_{01}: p_1 - p_0 = 0 \text{ versus } H_{11}: p_1 - p_0 > 0\}$ and

 $\{H_{02}: p_2 - p_0 = 0 \text{ versus } H_{12}: p_2 - p_0 > 0\}$

 p_0 , p_1 , and p_2 are the proportion of subjects on Trt0, Trt1, and Trt2, respectively, who are determined to have *histologically regressed*. Fisher's Exact Test will be used to assess if the data support rejecting the null hypothesis H_{01} , and likewise for H_{02} . To control Type I error, we will use a conservative Bonferroni adjustment for multiple comparisons with one-sided $\alpha = (0.05)/2 = 0.025$ as the significance level for each test. Rejection of a particular null hypothesis suggests superior efficacy of that specific treatment compared to control. Exact 95% confidence intervals will be calculated for p_1 - p_0 and for p_2 - p_0 . Confidence intervals for 'risk ratios' (p_1/p_0 , p_2/p_0) in addition to 'risk differences' (p_1 - p_0 , p_2 - p_0) may also be estimated. The main analysis will use the **modified ITT analysis set**. Sensitivity analyses for the same statistical method using the **modified ITT completers** and/or **per protocol analysis sets** may also be provided.

HIC#: 1603017415 Protocol version 11.0

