15.8 Sample Size Justification

Anticipated annual accrual is approximately 40-45 subjects.

Our general philosophy regarding Phase II trials of new drug combinations is to facilitate the prompt discovery of inactive agents, yet allow for a reasonable estimate of the response rates for those regimens demonstrating some degree of activity. However, excessive accrual to inactive study regimens to document precise response rates is to be avoided. The purpose of this study is to evaluate the activity and potential toxicity of the combination therapy of Imiquimod + HPV vaccine in subjects with untreated high-grade CIN 2,3 cervical dysplasia. This study will implement a 3 arm randomized trial design that will allow us to estimate the treatment effect of Imiquimod + HPV vaccine compared to observation as well as Imiquimod alone compared to observation.

Based on published literature for the primary outcome,³⁸ we assume a 28% spontaneous histological regression rate in CIN 2-3 lesions with observation alone (control group). From Grimm et al.'s efficacy

HIC#: 1603017415 Protocol version 11.0

trial of imiquimod for treatment of CIN 2-3, we would like to have sufficient power to detect a 35% absolute increase in rate of histologic regression in the imiquimod only arm compared to control. Based on this data, we consider a conservative effect size estimate also of an absolute 35% higher rate of histologic regression in the imiquimod + HPV vaccine intervention arm compared with the control arm. We therefore aim to recruit a total sample size of 114 subjects (38 in each arm). Calculations based on Fisher's Exact Test indicate we will have $\geq 90\%$ power to detect a treatment effect of $\geq 29\%$ in both treatment arms independently compared to the observation arm ($\alpha = 0.025$ for each comparison to control). In addition, with n = 38 subjects per arm, we would have 80% power to detect a treatment effect size of $\geq 25\%$ in one treatment arm compared to placebo (while maintaining 90% power to detect the treatment effect size of $\geq 25\%$ in the other arm). Assuming a subject dropout rate of 20%, a total sample size of 138 (n = 46 per arm) subjects is calculated which will be recruited over 5 years.

Some operating characteristics of the study design are as follows:

Exact Operating Characteristics for the Treatment Effect Size Δ given control group rate=0.28, n=38 subjects per arm, one-sided α

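### Fixed Bonferroni testing at one-sided 0.025 gives up power for the second of two real effects that Holm's step-down would keep under the same 0.05 family-wise bound

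*Combined protocol and SAP*

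**What the plan says.** Section 15.5 (Analysis for the Primary Objective) sets two co-primary comparisons with control: imiquimod plus HPV vaccine, and imiquimod alone. Both have one-sided alternatives, and for each "Fisher's Exact Test will be used to assess if the data support rejecting the null hypothesis". On multiplicity it states: "we will use a conservative Bonferroni adjustment for multiple comparisons with one-sided" α of 0.05/2 = 0.025 per test. The two results are read separately: "Rejection of a particular null hypothesis suggests superior efficacy of that specific treatment compared to control". Exact 95% confidence intervals for the two risk differences accompany the tests.

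Section 15.1 (General Statistical Considerations) sets a general type I error of 0.05 and adds: "Only the primary analysis will use an adjustment for multiple comparisons". Its general planning standard for power is "Type II error will be based on $\beta = 0.10$, unless otherwise specified". No step-down or other sequential procedure is mentioned in either section.

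Section 15.8 (Sample Size Justification) assumes 28% regression on observation and an absolute increase of 35 points in each active arm. It aims for 38 subjects per arm, raised to 46 for 20% dropout. Its operating-characteristics table gives power 0.8269 at a 35-point effect with α ≤ 0.025.

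**The concern.** Both comparisons are primary objectives (1.1.1 and 1.1.2), and each is claimed on its own result. Bonferroni holds each at 0.025 whatever happens to the other. Holm's procedure tests the smaller p-value at 0.025 and, only if that rejects, tests the larger at 0.05. It has the same guaranteed family-wise bound under any dependence between the tests, so the shared control arm does no harm. It also rejects everything that Bonferroni rejects.

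The plan expects the same effect in both active arms, a situation in which the second step is often reached. What is at stake is failing one of two stated primary objectives when both treatments work, because of a result with a one-sided p-value between 0.025 and 0.05.

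**Working it through.** **Inputs.** Control rate 0.28, both active arms 0.28 + 0.35 = 0.63, and 38 per arm (15.8). One-sided Fisher's exact test at 0.05/2 = 0.025 (15.5). Dropout 20% from 46 per arm (15.8): 46 × 0.80 = 36.8, so 36 to 37 evaluable.

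**Method.** Exact enumeration over the three binomial counts, with the control count shared by both tests.

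- Bonferroni rejects H₀₁ if p₁ ≤ 0.025, and likewise for H₀₂.
- Holm rejects H₀₁ if p₁ ≤ 0.025, or if p₂ ≤ 0.025 and p₁ ≤ 0.05, and symmetrically for H₀₂.

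**Step 1: reproduce the plan's figure.** Power per comparison at 0.28 versus 0.63, n = 38, α ≤ 0.025, comes out at 0.8269, equal to the table in 15.8. The other entries checked in that row also agree (0.6860 at 0.30, 0.7472 at 0.32, 0.8706 at 0.37, 0.9215 at 0.40).

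**Step 2: both arms work (0.63 each).**

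| Evaluable per arm | Per comparison, Bonferroni | Per comparison, Holm | Both significant, Bonferroni | Both significant, Holm | At least one, either method |
|---|---|---|---|---|---|
| 38 | 0.8269 | 0.8719 | 0.7229 | 0.8129 | 0.9308 |
| 37 | 0.8084 | 0.8644 | 0.6973 | 0.8093 | 0.9195 |
| 36 | 0.7885 | 0.8585 | 0.6706 | 0.8106 | 0.9065 |

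The columns tie together. At n = 38 the gain per comparison is 0.8719 − 0.8269 = 0.0450. This is the probability that the other test rejects at 0.025 while this one falls between 0.025 and 0.05. It can happen in either order, so the gain in both-significant is 2 × 0.0450 = 0.0900, and 0.7229 + 0.0900 = 0.8129. At least one significant is 2 × 0.8269 − 0.7229 = 0.9309 (0.9308 before rounding). Holm does not change it, because the first rejection always needs p ≤ 0.025. The chance of missing at least one of two real effects falls from 1 − 0.7229 = 27.7% to 1 − 0.8129 = 18.7%. The chance of missing both stays at 6.9%.

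**Step 3: unequal effects (35 and 25 points, n = 38).** Power for the weaker arm rises from 0.516 to 0.629, and for the stronger arm from 0.827 to 0.847.

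**Step 4: only one arm works (0.63 and 0.28, n = 38).** Power for the effective arm is 0.827 under either method. The chance of a false claim for the ineffective arm rises from 0.0147 to 0.0303.

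**Step 5: family-wise error (n = 38).** With both nulls true at 0.28, the chance of any rejection is 0.0269 under either method, and at most 0.028 over the rates scanned. With one null true, Holm's error is at most 0.033 over the rates scanned. All are below 0.05.

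**The case against.** The plan contains no error here. Bonferroni is valid and prespecified, and section 15.5 itself calls it conservative. Tests at one-sided 0.025 also sit at the same nominal level as the planned 95% intervals, so test and interval tell broadly the same story. Holm breaks that match at its second step. Every rejection it adds has a one-sided p-value between 0.025 and 0.05, so the 95% interval will generally include zero. An exact interval built differently from Fisher's test may disagree in some cases. Holm also roughly doubles the chance of a false claim for an ineffective arm when the other arm works.

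These costs are real and must be stated. They do not overturn the point. The false-claim risk stays inside the 0.05 that section 15.5 already accepts, and an interval not matched to a step-down test can be dealt with by saying so.

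Three stronger readings are tempting, and the documents do not support them.

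- A reader might infer that Bonferroni makes the trial more likely to miss any effect at all. It does not: the chance of at least one rejection is identical, and a single effective arm gains nothing.
- A reader might blame Bonferroni for the shortfall of 82.7% against the 90% standard. That shortfall is a sample-size matter. The prose of 15.8 claims at least 90% power at a 29-point effect, while its own table gives 0.8269 at 35 points. Holm at 38 per arm reaches 87.2%, so it does not close the gap.
- A reader might run the comparison at 46 per arm, where Holm passes 90% per comparison (89.5% to 93.8%). That assumes no dropout, whereas 15.8 assumes 20%.

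**Conclusion.** The point stands as an avoidable inefficiency, not as a fault in type I error control. If both active arms work as section 15.8 assumes, fixed Bonferroni costs 4.5 points of power per comparison and 9.0 points of the chance that both are significant at 38 per arm. At 36 to 37 evaluable per arm the costs are 5.6 to 7.0 points and 11.2 to 14.0 points. The loss concerns only the second rejection. The figures rest on a 28% control rate, equal 35-point effects, Fisher's one-sided test, and each null being interpreted separately. The contradiction between the power prose and the table in 15.8 is a separate matter and remains open whichever procedure is used.

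**What to change.** In 15.5, replace the Bonferroni sentence with Holm's procedure at family-wise one-sided 0.05: test the smaller of the two p-values at 0.025 and, if it rejects, test the other at 0.05; if the first does not reject, neither null is rejected. Keep the exact 95% intervals, and state that they are not matched to the second step and may include zero after a second-step rejection. Where 15.8 and its table refer to 0.025 per comparison, note that this is the first-step level.

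The change needs a few lines of text and no extra subjects. It should be dated and approved before anyone compares outcomes by arm, because relaxing a prespecified level afterwards would not be credible. The costs in inference are the interval mismatch and the rise from about 1.5% to 3.0% (at most about 3.3% over the rates scanned) in the chance of a false claim for one ineffective arm. If the sponsor prefers tests and intervals at the same level, keeping Bonferroni is defensible, but the plan should then say that this is the reason.

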15.6 Analysis for the Secondary Objectives

The secondary objectives are:

- to estimate treatment efficacy of Imiquimod + HPV vaccine (Trt1) compared to control (Trt0), and likewise Imiquimod only (Trt2) compared to control (Trt0), for the **secondary outcome** *histologic remission* (*yes/no*) after completion of the 12 to 16 weeks imiquimod course. Exact 95% confidence intervals for p₁ p₀ and for p₂ p₀ will be calculated. The main analysis will use the **modified ITT analysis set**. Sensitivity analyses for the same statistical method using the **modified ITT completers** and/or **per protocol analysis sets** may also be provided.
- to estimate treatment efficacy of Imiquimod + HPV vaccine (Trt1) compared to control (Trt0), and likewise Imiquimod only (Trt2) compared to control (Trt0), for the **secondary outcome HPV** clearance (*yes/no*) after completion of the 12 to 16 weeks imiquimod course. Exact 95% confidence intervals for p₁ p₀ and for p₂ p₀ will be calculated. The main analysis will use the **modified ITT analysis set**. Sensitivity analyses for the same statistical method using the **modified ITT completers** and/or **per protocol analysis sets** may also be provided.
- to characterize treatment safety and tolerability using descriptive statistics (safety analysis set)

15.7 Exploratory/Correlative Objectives

To characterize the association of **T cell infiltration** into the cervical dysplasia (i.e. frequencies and anatomical distributions of CD4 and CD8 T cells within the CIN) and pre- and post-immune therapy responses to HPV16/18 E7 antigens in subject peripheral blood lymphocytes (PBL) and serum with **clinical outcomes** (histologic regression/remission) and **viral clearance**. T_{RM} frequencies ,distributions and responses will be measured within subjects (pre and post 'prime and pull'), and changes from baseline will be compared between the treatment groups at relevant time points. Descriptive summary statistics will be used to evaluate associations and ANOVA will be the used to test the statistical significance of associations. The main analysis will use the **modified ITT analysis set**. Sensitivity analyses for the same statistical method using the **modified ITT completers** and/or **per protocol analysis sets** may also be provided.

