5.3 Exploratory Objectives

- 5.3.1 In the translational research component of this study we are planning to systematically evaluate and compare T cell infiltration into the cervical dysplasia and correlate with clinical response. The ultimate goal being to determine if the prime and pull strategy of Imiquimod + HPV vaccine leads to the establishment of T_{RM} cells and if this correlates to clinical regression of high-grade cervical dysplasia. The pre- and post-treatment cervical biopsies will be examined to determine the frequencies and anatomical distributions of CD4 and CD8 T cells within the CIN. We will stain paraffin embedded tissue sections with antibodies to CD4 and CD8. These sections will be costained with well-established markers of human T_{RM} (CD69, CD103).³¹ The comparison of T_{RM} frequencies and distributions will be conducted both within the individual (pre and post prime and pull) as well as amongst the groups at the relevant time points. We will assess possible correlation between T_{RM} and viral clearance and clinical outcomes. Because the biopsy sample is quite limited in size, we will also collect cells from the endocervical cytobrush to analyze the local T cell populations. The protocol for isolating and analyzing T cells from cytobrush is well established.³² We will stain the collected CD4 and CD8 T cells with respect to their T_{RM} (CD69, CD103) phenotype, as well as ex vivo stimulation with HPV peptide pool (the same one used in the CFSE experiments briefly described below) and measuring TNF- α and IFN- γ secretion by intracellular staining.

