9.0 STUDY PARAMETERS

9.1 Observations and Tests

The following observations and tests are to be performed and recorded before, during, and after treatment:

	Pre-Treatment	Treatment Period	Post-Treatment Period	End of Treatment	3 and 6 Month Post End of Treatment
Study week		8	16	22	
Study Procedures Window (weeks)	-10	± 1	+ 2	± 2	± 2
History, PE w/ pelvic exam	X	X	X	X	
Vital signs	X	X	X	X	
Urine pregnancy test	X**	X	X	X	
Pap				X	
High risk HPV test	X***			X	X
HPV 16/18 genotype	X		X	X	
Cytobrush collection*	X	X	X	X	
Colposcopy, cervical biopsy	X	X (biopsy if clinically indicated)	X (biopsy if clinically indicated)	X	
Peripheral blood sample collection*^	X****	X	X	X	
Toxicity assessment	X	X	X	X	
Randomization	X****				

- * For translational studies. Translational blood may be drawn after randomization but must be drawn prior to treatment.
- ^ See Section 6.2.1 for collection information.
- ** Urine pregnancy test must be performed within 7 days of treatment
- *** If high-risk HPV DNA results are already available, this testing may not have to be repeated
- **** Week 22 visit will occur at least 3 weeks after last dose of therapy
- ***** Randomization to occur following confirmation of eligibility

HIC#: 1603017415 Protocol version 11.0

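### Section 15.7 compares changes from baseline in T-cell and E7-response measures between arms without adjusting for the baseline value, although that value is collected

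*Combined protocol and SAP*

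**What the plan says.** Section 15.7 sets two tasks for the T-cell and E7-response measures. One is to relate them to histologic outcome and viral clearance. The other is the comparison between arms: "changes from baseline will be compared between the treatment groups at relevant time points". The only inferential test follows in the next sentence: "ANOVA will be the used to test the statistical significance of associations".

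Section 5.3 describes the same comparison as one made within the individual "as well as amongst the groups at the relevant time points", with no model. Section 15.1 adds only a general fallback: "Should parametric methods be inappropriate, the analogous non-parametric methods will be used". None of the three sections mentions a baseline covariate, ANCOVA or a regression model.

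The baseline values are in the plan:
- Biopsy (5.3): "The pre- and post-treatment cervical biopsies will be examined to determine the frequencies and anatomical distributions".
- Blood (9.1): "Translational blood may be drawn after randomization but must be drawn prior to treatment".
- Cytobrush: a pre-treatment sample for translational work is listed in 6.2.1 and in the 9.1 schedule.

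After baseline, 6.2.2 and 9.1 schedule cytobrush and blood for all subjects at weeks 8, 16 and 22. Biopsies at weeks 8 and 16 are taken only if clinically indicated, so week 22 is the only systematic post-treatment biopsy.

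**The concern.** A change score subtracts the whole baseline value, as if a subject one unit higher at baseline were expected to stay one unit higher at follow-up. When the true slope is below one, as it is for noisy measurements with similar spread before and after, this subtracts too much and adds baseline noise to the contrast. ANCOVA estimates the slope from the data.

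Section 5.3.1 makes it the ultimate goal of the translational work to learn whether prime and pull establishes tissue-resident memory T cells and whether this tracks with regression. The between-arm comparison of these measures bears directly on the first part. The trial is sized in 15.8 for the binary histologic endpoint alone, and the T-cell comparison has no power statement. Precision that needs no extra subject or sample is therefore worth having.

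**Working it through.** The documents state no figure for this comparison, so there is none to reproduce.

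**Inputs.** From 15.8: 38 evaluable subjects per arm. From 15.1: type I error 0.05; sidedness for exploratory tests is not stated, so two-sided is assumed. Not in the documents and therefore assumed: the correlation ρ between baseline and post-treatment value (0.3 to 0.9), the baseline SD s0 and post-treatment SD s1, a common slope across arms, and an illustrative true difference of 0.5 SD.

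**Step 1. Variance per subject.**
- Change score: s0² + s1² − 2ρ·s0·s1
- ANCOVA: s1²(1 − ρ²)
- Difference: s0² − 2ρ·s0·s1 + ρ²·s1² = (s0 − ρ·s1)², which is never negative.

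So, apart from the degree of freedom spent on the slope, ANCOVA cannot be less precise under this model. The two tie only when ρ·s1 = s0, that is, when the slope is exactly one.

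**Step 2. Equal variances (s0 = s1 = σ).** The change-score variance is 2σ²(1 − ρ) and the ANCOVA variance is σ²(1 − ρ²), so their ratio is (1 + ρ)/2. Change-score precision equal to that of ANCOVA with 38 per arm needs 38 divided by the ratio. Power for 0.5 SD and the difference detectable with 80% power use a normal approximation with standard error √(2 × variance / 38).

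| ρ | ratio | reduction | equivalent n per arm | power, change → ANCOVA | detectable difference (SD) |
|---|---|---|---|---|---|
| 0.3 | 0.65 | 35% | 58.5 | 45% → 63% | 0.76 → 0.61 |
| 0.5 | 0.75 | 25% | 50.7 | 59% → 71% | 0.64 → 0.56 |
| 0.7 | 0.85 | 15% | 44.7 | 80% → 86% | 0.50 → 0.46 |
| 0.9 | 0.95 | 5% | 40.0 | over 99% for both | 0.29 → 0.28 |

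A simulation of three arms of 38 (4,000 trials per correlation) gave ratios of 0.67, 0.74 and 0.87 at ρ = 0.3, 0.5 and 0.7. Both estimators averaged 0.50 against a true difference of 0.5, so neither is biased over repeated randomisations.

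**Step 3. Unequal variances (s0 = 1).**
- s1 = 1.5: change variance 3.25 − 3ρ = 2.35, 1.75, 1.15 at ρ = 0.3, 0.5, 0.7; ANCOVA variance 2.25(1 − ρ²) = 2.05, 1.69, 1.15. Reductions are about 13%, 4% and 0%.
- s1 = 2: change variance 5 − 4ρ = 3.8, 3.0, 2.2; ANCOVA variance 4(1 − ρ²) = 3.64, 3.00, 2.04. Reductions are about 4%, 0% and 7%.

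**Step 4. An observed imbalance.** With equal variances, given a baseline difference d between two arms, the change-score contrast is expected to miss the true effect by −(1 − ρ)d. One standard error of the baseline difference at 38 per arm is √(2/38) = 0.23 SD. An imbalance of that size shifts the contrast by 0.16, 0.11, 0.07 and 0.02 SD at ρ = 0.3, 0.5, 0.7 and 0.9. ANCOVA removes this shift.

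**The case against.** Several objections have force.

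- **The named test may not belong to this comparison.** The ANOVA sentence is about associations, and the section opens by defining these as associations with clinical outcomes and viral clearance. A reader might infer that the plan prescribes ANOVA of change scores between arms, but the text does not literally say so. It is the natural reading, because no other test is named. If it is not meant, the comparison has no stated model, and the same edit fills that gap.
- **Change scores are a valid choice.** A reader might infer that they are biased. Under randomisation they are not. The case rests on precision, and on the shift conditional on an observed imbalance.
- **The gain may be small.** The treatment is meant to draw T cells into tissue that section 2.0 calls restrictive, so post-treatment spread may well grow. Step 3 shows the gain can then largely vanish. A log scale may bring the variances closer, but the documents do not settle this.
- **The 15.1 fallback may apply.** If skewed data lead to a non-parametric test, the normal-theory ratios no longer describe the planned analysis. That fallback mentions no baseline adjustment either.
- **Few samples per arm cannot be asserted.** A reader might expect assay failures to thin the data. The documents give no failure rate; 5.3.1 says only that biopsy material is limited in size and adds cytobrush sampling for that reason.

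The first four limit how firmly the point can be stated, and the last removes an argument from it. None gives a reason to leave a collected baseline value out of the model.

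**Conclusion.** The point holds as a minor one. Section 15.7 plans a between-arm comparison of changes, names no baseline covariate, and would generally get a more precise answer from ANCOVA with data already collected. With equal variances the reduction in variance runs from 35% at ρ = 0.3 to 5% at ρ = 0.9. With a larger post-treatment SD it can be close to nil. The actual size is unknown, because the documents give neither SD nor correlation.

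A reader should not infer any threat to the trial's main results. The objective is exploratory and has no power statement. Section 15.1 leaves it outside multiplicity control ("Only the primary analysis will use an adjustment for multiple comparisons"), and neither the sample size nor any primary or secondary conclusion depends on it.

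**What to change.** In 15.7, state that the between-arm comparison of T-cell and E7-response measures uses ANCOVA of the post-treatment value on treatment group and baseline value, on the log scale, or rank-based if the data are skewed. Apply it at week 22 for biopsy measures and at each scheduled post-baseline visit (weeks 8, 16 and 22) for cytobrush and blood measures. Say separately which test serves the associations with clinical outcome and viral clearance.

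The cost is a few lines of SAP wording, to be settled before the data are analysed, and one degree of freedom per model. Samples, visits and software stay the same. No further subjects are lost, since a change score already requires the baseline value.

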mice, this strategy reduces spread of infectious viruses and prevents clinical disease. These results strongly suggest the possibility of inducing T cell responses against oncogenic HPV genotypes through immunization with a prophylactic HPV vaccine, followed by recruitment of HPV-activated T cells into cervical lesions using a local immune-response modulator.

Imiquimod, a topical immune response modulator, has antiviral and antitumor activity, induces cytokines including interferon, tumor necrosis factor, and interleukins 1, 6, and 8, and activates T cells triggering an immune response associated with HPV clearance. Indicate Image Image

We believe that "prime and pull" will provide further protection to imiquimod treatment alone, by eliciting robust T cell responses that can be pulled into the genital mucosa using chemokines induced by imiquimod application. Currently, a 9-valent prophylactic HPV vaccine (9vHPV) is commercially available and provides protection against 7 high-risk HPV types that cause 90% of all cervical cancers (and protects against 2 additional HPV types that cause 90% of all genital warts). ²² 9vHPV is a sub-unit protein vaccine; vectors expressing the papillomavirus *L1* gene have been used to generate virus like particles (VLPs) that mimic the wild type virus capsid morphologically and antigenically but contain no DNA and are therefore noninfectious. This vaccine is highly immunogenic, inducing a robust serum neutralizing antibody response which prevents incident infection. ^{25,26} Previous studies have demonstrated induction of antigen-specific T cell responses by prophylactic HPV vaccines as well. ²⁷⁻³⁰

Published treatment efficacy with imiquimod²⁴ and the preclinical in vitro data presented above and fully reported in *Nature*¹⁸ clearly suggest that a "prime and pull" vaccination strategy may provide significant therapeutic effect for HPV-associated CIN 2/3 lesions. Because the development of a novel, effective treatment modality without the need of destructive interventions on the cervix in CIN 2/3 remains an unmet medical need, in this study we are planning a multi-arm randomized clinical trial to determine the therapeutic clinical effect and resulting immune response of a "prime and pull" method of treatment in women with CIN 2-3 lesions using imiquimod vaginal suppository in conjunction with the commercially available 9-valent HPV vaccine.

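### Section 15.7 does not put treatment arm into the T cell-to-outcome test; if arms are pooled, an imiquimod effect on both can appear as an association

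*Combined protocol and SAP*

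**What the plan says.** Section 15.7 sets out to relate T cell infiltration in the lesion, and E7 responses in blood and serum, to histologic regression or remission and to viral clearance. The method is one sentence: "Descriptive summary statistics will be used to evaluate associations and ANOVA will be the used to test the statistical significance of associations". No factor, covariate or stratum is given.

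Arm does appear in 15.7, but for a different question: "changes from baseline will be compared between the treatment groups at relevant time points". Section 5.3 keeps the same separation. It plans T_RM comparisons within women and among groups, and then adds: "We will assess possible correlation between T_{RM} and viral clearance and clinical outcomes". It describes the ultimate goal as learning whether prime-and-pull "leads to the establishment of T_{RM} cells and if this correlates to clinical regression of high-grade cervical dysplasia".

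The main analysis set for 15.7 is modified ITT. Section 15.1 sets alpha at 0.05 and states: "Only the primary analysis will use an adjustment for multiple comparisons".

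**The concern.** The plan's own rationale makes arm a likely common cause of both variables. Section 2.0 says imiquimod "activates T cells triggering an immune response associated with HPV clearance" and expects imiquimod-induced chemokines to draw primed T cells into genital tissue. Section 15.8 assumes 28% regression under observation and 35 percentage points more in each imiquimod arm. If the drug does both, women who regress will mostly be women who received imiquimod, and they will have more local T cells for that reason alone.

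A pooled test cannot tell T cells that track regression from a drug that moved both. The problem is largest when imiquimod works, which is also when a mechanistic claim would be made. At stake is the reading of the translational result, not the efficacy result.

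**Working it through.** **Inputs from the documents.** Regression 0.28 / 0.63 / 0.63 (0.28 + 0.35 in each imiquimod arm) and 38 evaluable women per arm, 114 in total (15.8); alpha 0.05 (15.1).

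**Assumptions.** The ANOVA F test is non-directional. The T cell change is normal with SD 1 within arm. Imiquimod shifts its mean by δ, taken from 0 to 1.5 SD because the documents give neither size nor SD. Within each arm, T cells and outcome are independent, so T cells play no role.

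**Plan's own figure.** Section 15.7 states none. The nearest figure with the same rates and sample size is in the 15.8 table: one-sided Fisher power for a difference of 0.35 at α ≤ 0.025, given as 0.8269. Exact enumeration of all 39 × 39 outcomes gives 0.8269, so the inputs are read as the plan uses them.

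**Arm mix by outcome (1:1:1 allocation).**
- Regressors on imiquimod: (0.63 + 0.63) / (0.28 + 0.63 + 0.63) = 1.26 / 1.54 = 0.818.
- Non-regressors on imiquimod: (0.37 + 0.37) / (0.72 + 0.37 + 0.37) = 0.74 / 1.46 = 0.507.
- Expected pooled difference in the T cell measure: (0.818 − 0.507) × δ = 0.311 δ, with no within-arm association.

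**Hand check at δ = 1.**
- Expected regressors: 114 × 1.54/3 = 58.5; non-regressors: 55.5.
- Variance among regressors: 1 + 0.818 × 0.182 = 1.149. Among non-regressors: 1 + 0.507 × 0.493 = 1.250.
- SE = √(1.149/58.5 + 1.250/55.5) = 0.205.
- Standardised difference: 0.311 / 0.205 = 1.52. Rejection at two-sided 5% is about Φ(1.52 − 1.96) = Φ(−0.44), or 33%.

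**Simulation (20,000 trials per scenario).** ANOVA of the T cell change on regression (yes/no), without and with arm as a factor:

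| Assumed shift δ (SD) | Rejects, pooled | Rejects, arm in model |
|---|---|---|
| 0 | 5.0% | 5.0% |
| 0.25 | 7.0% | 5.2% |
| 0.5 | 12.7% | 5.1% |
| 0.8 | 23.9% | 5.1% |
| 1.0 | 32.7% | 4.8% |
| 1.5 | 54.4% | 5.0% |

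**Sensitivity of the pooled rate.**
- Smaller drug effect on outcome (0.28 / 0.48 / 0.48, assumed): 7.0% at 0.5 SD and 14.2% at 1.0 SD.
- No drug effect on outcome (0.28 in all arms): 5.1% at 0.5 SD and 5.2% at 1.0 SD.
- All 46 recruited per arm evaluable: 14.4% at 0.5 SD and 38.7% at 1.0 SD.
- Controls absent, equal rates in the two imiquimod arms (0.63 / 0.63), extra vaccine-arm shift of 0.5 or 1.0 SD: 4.6% and 5.1%.
- Controls absent, vaccine arm at 0.73 (assumed), same extra shifts: 5.6% and 7.0%.

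**The case against.** Five points can fairly be made for the plan.

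- **Silence is not exclusion.** A reader might infer that 15.7 deliberately leaves arm out. It does not say so. The sentence just before the ANOVA sentence compares changes between groups, and ANOVA would suit that comparison. This stands: the text is silent. But silence permits the pooled test and leaves the model to be chosen after the data are seen.
- **The named analysis set may hold no controls.** As defined in 15.2, modified ITT requires a dose of study drug, and the control arm receives none (6.2.1). Read literally, only the imiquimod arms remain and the inflation largely disappears. However, 15.5 uses the same set to compare each treatment with control, so dropping controls is probably unintended. The two sections must be reconciled.
- **Whose 5%?** A reader might infer that the planned test breaks its 5% error rate. When arm drives both variables, the marginal association is real, and the pooled test correctly rejects a marginal null. The rate fails only against the null of no association within arms, which 15.7 never states. The concern is therefore that a marginal association is read as mechanism.
- **Not every immune measure is exposed.** Pre-treatment values cannot be caused by randomised arm. The rationale concerns recruitment to genital tissue, and the documents do not say that imiquimod shifts E7 responses in blood or serum. The argument is strongest for post-treatment and change-from-baseline local T cell measures.
- **It is exploratory.** No primary, secondary or safety conclusion depends on it. This stands and limits the weight of the point, but the correlation with regression is part of what section 5.3 calls the goal of the translational work.

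**Conclusion.** The concern holds in a conditional form. Section 15.7 neither includes arm in the T cell-to-outcome test nor stratifies by it. If observation and imiquimod arms are pooled, as the control comparisons in 15.5 imply, and imiquimod affects both local T cells and outcome, as the plan expects, the pooled ANOVA will show associations that do not exist within any arm. At the planned rates it rejects in about 13% to 54% of trials for assumed shifts of 0.5 to 1.5 SD, against about 5% with arm in the model. With a 20-point rather than a 35-point effect on regression, the rate is about 7% at 0.5 SD and 14% at 1.0 SD.

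A reader might infer that a spurious correlation is certain. The documents do not support that: they give no size for the T cell effect, and with no effect of imiquimod on either T cells or outcome the pooled rate stays near 5%. Nor does the point touch the efficacy analysis.

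**What to change.** In section 15.7, state that each association between a post-treatment or change-from-baseline immune measure and regression, remission or viral clearance will be tested in a model that includes arm. This can be an ANOVA of the measure on outcome plus arm. Logistic regression of outcome on the measure plus arm is an alternative; it is a different model, so one should be named in advance. Report arm-specific estimates beside the adjusted result. State that unadjusted pooled associations are descriptive only and will not be used to support the mechanism.

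In section 15.2, reconcile the dosing requirement of modified ITT with the observation arm, so that it is clear whether controls are in this analysis.

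The cost is a few sentences and two degrees of freedom: residual degrees of freedom fall from 112 to 110 with 114 women. Adjusting for arm does not prove mechanism, because other causes shared within an arm remain, but it removes the part that arm alone would produce.
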